5.2 Subject Preparation

Study staff will confirm that the subject is eligible and complies with applicable site requirements prior to starting study procedures.

Study Title: U-TruSignal SpO₂ Testing in Neonates

Study No: 123.04-2017-GES-0002

After providing consent, no preparation beyond the investigational site's standard of care is required before study procedures.

5.3 Description of Study Procedures

The following are the steps to be performed:

- 1) To document the case, photographs of the position of the measurement sensors and other equipment may be taken at the request of the Sponsor at any point of the procedure, when necessary.
Note: photographs are taken in a way that the subject cannot be identified from the pictures.
- 2) Apply sensor(s) to the subject as appropriate. No more than one SpO₂ sensor placed on the same limb, and no sensor placed close to blood draw site/IV cannulation (same limb). Record site of sensor(s) placed on the CRF.
- 3) Allow the clinical environment and readings to stabilize.
- 4) Start data collection using the data collection tool.
- 5) Collect data using the data collection tool for a minimum of 10 minutes prior to routine arterial blood draw, per the data collection tool. Record possible accidental annotations in CRF.
Note: The arterial blood draw collected during this study will be performed according to the site's standard of care and will not be prescribed by the Sponsor.
- 6) When routine arterial blood draw is conducted, mark arterial blood draw time with data collection tool. The blood sample will be processed through hospital's standard procedure. Record possible accidental annotations in CRF.
- 7) After arterial blood draw, continue collecting data using the data collection tool for a minimum of 2 minutes. Record possible accidental annotations in CRF. Stop data collection.
- 8) Remove sensor(s) from the subject.
- 9) Monitor and record the following information using the data collection tool or recording on CRF during steps 4-7):
 - a. clinical status notes; i.e., frequent apnea, hemodynamic instability, abnormal heart rhythm, or other status;
 - b. environmental conditions such as changes in lightning conditions, ongoing care moving the neonate outside blood sampling, excessive clinical signs such as agitation, readjustment of a sensor; AND
 - c. notes regarding data collection such as accidental annotations.
- 10) Obtain results of the arterial blood draw and record possible errors during standard procedure for blood sampling and analysis.
- 11) Repeat Steps 1-10 up to 3 times to obtain a maximum of 6 data pairs, 3 data pairs per sensor aiming to collect equal data for each sensor.

Note: Alternate the sensors used; e.g., if TS-AF was used first, then TS-SE should be used at the next data collection.

NOTE: Study Completion or Subject's End of Study is defined as the last data collection determined by the Investigator and /or study staff by recording the study completion date and time.

GE Healthcare engineering representatives may be present during study procedures, depending upon their need to observe the functioning of the investigational device (their need to observe will depend upon the study staff indicating there is an issue for the engineers to look at). These representatives will always be accompanied by study staff. These visits will be agreed upon and arranged by the Research Manager and the Investigator on a case-by-case basis.

Study Title: U-TruSignal SpO₂ Testing in Neonates

Study No: 123.04-2017-GES-0002

5.4 Follow-up

No follow-up will be conducted. The subject will be followed for AEs from the time consent has been provided to study completion/end of study. (See definition of study completion.)

6. STUDY DATA COLLECTION AND ASSESSMENTS

6.1 Primary Assessment

The Investigator or designated study staff will perform the collection of SpO₂ and pulse rate, that will be recorded in the U-TruSignal Data Collector. Laboratory results from arterial blood draw will be collected from the hospital's medical records.

The following data will be collected on the CRF:

- 1) Demographics: date of birth, gender, length, and weight, skin tone (see Appendix C – Modified Fitzpatrick Scale);
- 2) U-TruSignal Serial Number, Sensor Type, LOT Number, and Attachment Location of the Sensor;
- 3) Notes regarding data collection e.g. incorrect annotation of data file or several data files;
- 4) Relevant information on the clinical status affecting hemodynamic stability such as frequent apnea, hemodynamic instability, abnormal heart rhythm;
- 5) Environmental conditions e.g. open bed, changing lightning conditions, ongoing care causing movements, readjustment of a sensor.

The laboratory results will include and to be collected from the hospital's medical record:

- 1) Co-Oximeter information,
- 2) Functional SaO₂ (%),
- 3) Fractional oxyhemoglobin (FO₂Hb) [%],
- 4) Fractional carboxyhemoglobin (FCOHb) [%],
- 5) Fractional methemoglobin (MetHb) [FMetHb] [%],
- 6) Total hemoglobin (tHb) (ctHb) [g/L]
- 7) Fetal hemoglobin (Hb) [g/L] (calculated), and
- 8) Fractional fetal hemoglobin [%].

6.2 Safety Assessments

The description, severity, and device relatedness of any AE or SAE during the study will be recorded. Subjects will, if necessary, be provided with emergency care. In the event of any device issues, the event will be recorded. Safety reporting will be conducted as described in this protocol.

7. QUALIFICATION AND TRAINING PLAN

7.1 Staff Qualifications

All members of the study staff participating in the conduct of the clinical investigation shall be qualified by education, training and/or experience to perform their tasks, and this shall be documented appropriately, as per ISO 14155:2011 for clinical studies.

7.2 Training Plan for the Protocol and Research Device/Product

Before starting the study, the study staff and hospital department staff will be trained on the clinical investigation requirements set forth in this study protocol according to the following requirements.

- Title of Training

Study Title: U-TruSignal SpO₂ Testing in Neonates

Study No: 123.04-2017-GES-0002

- Training objectives
- Training logistics (who conducts training and training method)
- Target audience (who will be trained)
- Training content (including device operation and set-up, protocol review and understanding) Any personnel that will be involved in the study must receive protocol training prior to participating in the study. Additional training may be provided as needed.

Study staff directly operating or maintaining the research device will be trained based on the operator manual and/or qualified based on experience as qualified by the hospital/clinical site policy. A training log will be provided and maintained for the study.

The Principal Investigator will be ultimately responsible for execution of this study in accordance with the protocol and for device/product use in this study by members of the study staff.

8. SAFETY

8.1 Anticipated Adverse Events

Being in this study involves some foreseeable risks.

Pulse Oximetry Sensor placement involves positioning pulse oximetry sensors on the volunteer subject in the same manner used with released SpO₂ cables. The U-TruSignal investigational device is not in direct contact with the patient. The sensors that will be in contact with the subject are cleared for commercial use. The sensors may be warm to the touch. Under normal operating conditions (no fault conditions), the sensors are not expected to overheat. If the Investigator or delegate conducting the study senses the sensor is too warm or the subject is experiencing discomfort the sensor will be removed immediately and the area of concern will be massaged, and the sensor will be replaced at the discretion of the study staff, the sensor may be removed, and the study procedures discontinued at any time. Sensors may cause irritations to the skin in some subjects. The risk in the use of pulse oximetry sensors is considered minimal.

There is always a chance of unexpected risks. Throughout the study, the Sponsor will evaluate and update safety information in study documents.

8.2 Adverse Event Definitions

Adverse Event (AE): any untoward medical occurrence, unintended disease or injury, or untoward clinical signs (including abnormal laboratory findings) in subjects, users or other persons, whether or not related to the investigational medical device [ISO 14155:2011 3.2]. This includes events related to the investigational device or the comparator and to the procedures involved. For users or other persons, this is restricted to events related to the investigational medical device.

Serious Adverse Event (SAE): an AE that led to death; led to a serious deterioration in the health of the subject, that either resulted in a life-threatening illness or injury, a permanent impairment of a body structure or a body function, or in-patient or prolonged hospitalization, or medical or surgical intervention to prevent life-threatening illness or injury or permanent impairment to body structure or a body function; or led to fetal distress, fetal death or a congenital abnormality or birth defect. Planned hospitalization for a pre-existing condition, or a procedure required by the protocol without serious deterioration in health, is not considered a SAE [ISO 14155:2011 3.37].

Adverse Device Effect (ADE): an AE related to the use of an investigational medical device [ISO 14155:2011 3.1]. This includes any AEs resulting from insufficient or inadequate instructions for use, deployment, implantation, installation, or operation, or any malfunction of the investigational medical device. This includes any event that is a result of a user error or intentional misuse of the investigational device [ISO 14155:2011 3.43].

Study Title: U-TruSignal SpO2 Testing in Neonates

Study No: 123.04-2017-GES-0002

Serious Adverse Device Effect (SADE): an ADE that has resulted in any of the consequences characteristic of a SAE [ISO 14155:2011 3.36].

Device deficiency: an inadequacy of a medical device with respect to its identity, quality, durability, reliability, safety, or performance, such as malfunctions, use errors, and inadequate labeling [ISO 14155:2011 3.15].

Unanticipated serious adverse device effect (USADE): a SADE, which by its nature, incidence, severity, or outcome has not been identified in the current version of the risk analysis report [ISO 14155:2011 3.42]. In the United States, any serious adverse effect on health or safety or any life-threatening problem or death caused by, or associated with, a device, if that effect, problem, or death was not previously identified in nature, severity, or degree of incidence in the study documents, will be reported in accordance with 21 CFR §812.3 and applicable laws and regulations.

8.3 Documentation of Safety Events

All AEs, including all SAEs, are required to be collected, investigated, and documented during the study reporting period, as defined in the study procedure set forth in this protocol. Documentation will include:

- Description of Event
- Date of onset and resolution
- Severity (mild, moderate, or severe)
 - *Mild:* Symptom(s) barely noticeable to the subject or does not make the subject uncomfortable. The AE does not influence performance or functioning. Prescription drugs are not ordinarily needed for relief of symptom(s).
 - *Moderate:* Symptom(s) of a sufficient severity to make the subject uncomfortable. Performance of daily activities is influenced. Treatment of symptom(s) may be needed.
 - *Severe:* Symptom(s) of a sufficient severity to cause the subject severe discomfort. Treatment for symptom(s) may be given.
- Serious (yes/no)
- Causal relationship to investigational medical device? (not related, possibly related, or related)
 - *Not related:* The AE is reasonably expected to be related to (or caused by) a concurrent illness, effect of another device/drug or other cause, and is unlikely related to the investigational product.
 - *Possibly related:* The AE is reasonably expected to be related to the investigational product, and an alternative etiology is equally or less likely compared to the potential relationship to investigational product.
 - *Related:* There is a strong relationship to investigational product or recurs on re-challenge, and another etiology is unlikely or there is no other reasonable medical explanation for the event.
- Treatment given and/or action taken (procedure stopped, withdrawn from study, or no action)
- Anticipated (yes/no)

8.4 Reporting of Safety Events

The following events are to be reported to the Sponsor within 72 hours of the event occurrence and to the EC per their policy:

- All SAEs and USADEs
- All device issues that could possibly lead to an SAE

The following information is the Sponsor contact for SAEs and/or UAEs:

[name]

Study Title: U-TruSignal SpO2 Testing in Neonates

Study No: 123.04-2017-GES-0002

[contact] hours)

E-mail: [contact]

Additional follow-up information including the medical records of the subject may be requested by the Sponsor. In addition, safety information may be shared with regulatory agencies and other participating sites, as required by applicable law and regulation.

8.5 Device Deficiencies/Complaints

Device deficiencies related to the investigational device should be reported directly to the engineering team, after each case by the Investigator or study staff, who finishes the case. Device deficiencies related to the approved or cleared device should be reported to the study Sponsor.

Sponsor contact for device complaints:

[name], *Clinical Affairs Project Manager*

[contact]

E-mail: [contact]

All device deficiencies will be collected, fully investigated, and documented in the source document and appropriate CRF during the study reporting period. The Principal Investigator is responsible for notifying the Sponsor if there is any device issue that could potentially lead to a SAE.

9. ETHICAL CONDUCT OF THE STUDY

The study will be carried out in accordance with the protocol and with principles enunciated in the current version of the Declaration of Helsinki; the guidelines of GCP for medical devices, as set forth by ISO 14155:2011 and ISO 14971:2012; European Directive on medical devices 93/42/EEC for studies conducted in Europe; and applicable local regulatory authority's requirements of Finland – Valvira.

The study will be conducted and reported in accordance with applicable policies of the local EC and governing regulatory authorities in Finland and India (when India's law comes into effect).

If national or regional EC requirements are less strict than the requirements of GCP, such as ISO 14155:2011 for medical devices, the Sponsor shall apply the requirements of this International Standard to the greatest extent possible, irrespective of any lesser requirements, and shall record such efforts.

9.1 Ethics Committee

The responsible Principal Investigator at each site will ensure that approval from an appropriately constituted EC is attained for the clinical study prior to enrolling subjects, and Principal Investigator will ensure that documentation of approval is maintained for the duration of the study.

The Principal Investigator will ensure that the Sponsor is notified of any withdrawal of EC approval within 5 working days of such occurrence. If approval is terminated or suspended, the Principal Investigator will promptly notify the Sponsor and provide written explanation.

9.2 Regulatory Agencies and Competent Authority(ies)

The Sponsor will obtain approval from the local regulatory agency or competent authority before the start of the clinical trial, if necessary, per applicable local laws and regulations. Any additional requirements imposed by the EC or regulatory authority shall be followed, if applicable. Documentation of notification will be maintained in the Site Regulatory Binder.

For clinical studies conducted in Finland, per the local regulatory agency or competent authority requirements the Sponsor will notify Valvira, the local regulatory agency or competent authority, before the start of the clinical trial, if necessary, per applicable local laws and regulations.

9.3 Management of Protocol Modifications and Amendments

Substantial amendments will only be implemented after approval of the EC.

9.4 Management of Protocol Deviations

A deviation is any instance(s) of failure to follow, intentionally or unintentionally, the requirements of the protocol. Under emergency circumstances, deviations from the protocol to protect the rights, safety, and well-being of human subjects may proceed without prior approval of the Sponsor and the EC. Such deviations shall be documented and reported to the Sponsor and the EC as soon as possible. Deviations will be reported as:

- **Critical Deviations:** Deviations that significantly affect the safety, efficacy, integrity, or conduct of the study. These deviations must be reported to the Sponsor no later than 5 working days from awareness of occurrence and reported to the EC per the deviation reporting policy.
- **Non-Critical Deviations:** Protocol deviations that do not significantly affect the safety, efficacy, integrity, or conduct of the trial. These deviations must be documented on the CRF Protocol Deviation page and will be reviewed by the study monitor.

Non-substantial modifications may be made during the normal course of device optimization, maintenance, and feasibility testing. Non-substantial modifications will be communicated to the CA as soon as possible, if applicable, and to the EC per their policy.

9.5 Participant Information and Informed Consent

The investigators will explain to each participant's parent(s) or LDR(s) the nature of the study, its purpose, the procedures involved, the expected duration of exposure to the investigational device, the potential risks and benefits, and any potential discomforts. Each participant's parent(s) or LDR(s) will be informed that participation in the study is voluntary, that he/she/they may withdraw his/her/their child from the study at any time, and that withdrawal of consent will not affect his/her/their child's subsequent medical assistance and treatment. The participant's parent(s) or LDR(s) must be informed that his/her/their child's medical records may be examined by authorized individuals other than their treating physician.

All participant's parent(s) or LDR(s) for the study will be provided an informed consent form, describing the study and providing sufficient information, to allow the participant's parent(s) or LDR(s): (i) to make an informed decision about his/her/their child's participation in the study, and (ii) to be fully aware of his/her rights under the applicable law. Informed consent documents will be subject to approval by the EC prior to enrolling subjects in the study.

The participant's parent(s) or LDR(s) should read and consider the statement before signing and dating the ICF and shall be given a copy of the signed document. The ICF must also be signed and dated by the Investigator (or his/her designee), and it shall be retained as part of the study records.

9.6 Early Termination of the Study

The Sponsor may terminate the study prematurely according to certain circumstances. Examples of such circumstances include ethical concerns, insufficient participant recruitment, participant safety concerns, alterations in accepted clinical practice that make the continuation of a clinical trial unwise, early evidence of benefit or harm of the research product, or for any other reason.

9.7 Incidental Finding

Incidental findings observed during the study conduct shall be processed under the purview of the Principal Investigator through the investigational site's standard of practice.

10. STATISTICAL METHODS

10.1 Statistical Hypothesis

Summary statistics will be used to summarize the data. No statistical hypothesis is being tested in this study.

10.2 Sample Size Determination

This study is to collect blood samples from neonates under normal clinical conditions. The minimum number of subjects is seventeen (17) subjects. Maximum total enrollment for the study is one hundred forty (140) subjects.

Per ISO 80601-2-61:2011, ⁷ at least 200 data pairs from at least 10 subjects is required for the adult desaturation test, with SaO₂ values distributed on 5 saturation plateaus spanning the range of 70-100%. Unlike the invasive controlled desaturation test on adults in a laboratory environment in which the SaO₂ can range from 70% to 100%, the SaO₂ collected in this study is expected to be around 90%. Since SaO₂ values in this study may be clustered in 1 plateau around 90%, a minimum of 50 data pairs is considered adequate to ensure proper function/clinical performance with neonates with U-TruSignal device. Up to 3 data pairs may be collected on an individual patient per sensor, patients with a minimum of one data pair will be included in the study. The TruSignal AllFit Sensor (model #TS-AF-25 or TS-AF-10) and TruSignal Sensitive Skin Sensor (model # TS-SE-3) will be used. The study is targeted to obtain 50 to 70 SpO₂/SaO₂ data pairs from 17 to 70 neonatal subjects per sensor.

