Background and Rationale:	
Pulse oximetry has the unique advantage of continuously monitoring the saturation of hemoglobin with oxygen; easily and noninvasively providing a measure of cardio-respiratory function.³ It is the preferred method of oxygen monitoring in neonates.²
 
At a neonatal intensive care unit (NICU), continuous health monitoring for the neonates provides crucial parameters for urgent diagnoses so that adequate medical treatment can be instituted.⁴ The goal of SpO₂ monitoring for premature neonates is to adequately deliver oxygen to the tissue without causing the complications of oxygen toxicity. Often, the SpO₂ readings from neonates are labile and difficult to keep within a narrow range.
 
The purpose of the study is to demonstrate proper function of the U-TruSignal device via clinical performance testing in a neonatal human subject population under standard clinical conditions.
 
A study with human subjects will provide the needed clinical evidence for assessing the accuracy of the pulse oximeter as recommended by the United States Food and Drug Administration (FDA) Guidance Document (entitled: "Pulse Oximeters – Premarket Notification Submissions [510(k)s]: Guidance for Industry and Food and Drug Administration Staff").

Procedures/ Methods:	
After providing consent, no preparation beyond the investigational site's standard of care is required before study procedures begin. At the start of the procedure, 1 to 2 sensors, upon the discretion of the Investigator, shall be applied to the subject. Record site/location of the sensors on the case report form. Allow readings to stabilize. After at least 10 minutes of data collection, collect arterial blood and analyze blood per hospital's standard procedure. Continue collection of data post blood draw for 2 minutes. Clinician shall monitor and record information as specified in this protocol and obtain results of arterial blood draw.
 
The duration of the subject's participation in the study is dependent upon how long the arterial cannula is required for the subject. The period of data collection during the scheduled routine arterial blood draw (up to 3 independent arterial blood draws) is a minimum of 10 minutes and up to approximately 30 minutes from the application of the sensor to the subject. A maximum of 6 data pairs (3 data pairs per sensor) can be collected from each subject.

Study Title: U-TruSignal SpO₂ Testing in Neonates

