4.2 Number Subjects

This study is intended to collect blood samples from neonates under normal clinical conditions. The minimum number of subjects is 17 subjects. Maximum total enrollment for the study is 140 subjects.

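### Does the minimum of 17 infants put the target of 50 data pairs per sensor at risk?

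*Combined protocol and SAP*

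**What the plan says.** Section 4.2 and the synopsis give the subject numbers: "The minimum number of subjects is 17 subjects", with a maximum enrolment of 140. Section 10.2 repeats both figures and gives the reasoning. SaO₂ is expected to cluster around 90%, so "a minimum of 50 data pairs is considered adequate to ensure proper function/clinical performance with neonates with U-TruSignal device". Each infant may give up to 3 pairs per sensor, and "patients with a minimum of one data pair will be included in the study". The section ends with the target: "The study is targeted to obtain 50 to 70 SpO₂/SaO₂ data pairs from 17 to 70 neonatal subjects per sensor".

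Three passages govern how many pairs an infant can yield:

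- Synopsis, Procedures/Methods: "1 to 2 sensors, upon the discretion of the Investigator, shall be applied to the subject".
- The same paragraph allows "up to 3 independent arterial blood draws".
- Section 5.3, step 11, sets a maximum of 6 pairs, "3 data pairs per sensor aiming to collect equal data for each sensor". The note under it says: "Alternate the sensors used; e.g., if TS-AF was used first, then TS-SE should be used at the next data collection".

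Section 10.3.2 analyses valid data only. Section 10.3.3 analyses each sensor type separately and lists the grounds for excluding a pair. Section 10.4 rules out imputation, and Section 10.1 states that no hypothesis is tested.

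**The concern.** The minimum equals the pair target divided by the largest yield an infant can give, with nothing added for loss. The protocol permits that yield but does not require it. An infant may wear one sensor, may have one or two draws, and still counts with a single pair. Section 10.3.3 then removes pairs for low perfusion, movement, waveform artefact, unstable SpO₂ and analyser errors, and Section 1 itself describes neonatal SpO₂ as labile. Some loss is to be expected.

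No section says whether the 50 pairs are counted before or after those exclusions, or that enrolment continues until each sensor has 50. Read literally, a study could stop at 17 infants, satisfy Section 4.2, and report the primary ARMS for one or both sensors on fewer pairs than Section 10.2 aims for. The pair count is the only adequacy criterion the plan states for that estimate, so a shortfall would matter.

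**Working it through.** **Inputs.** From Section 10.2: 50 to 70 pairs and 17 to 70 subjects per sensor; 1 to 3 pairs per infant per sensor; study-wide minimum 17 and maximum 140. From the synopsis: 1 or 2 sensors, up to 3 draws. The documents give no loss rate, so the rates below are assumptions.

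**1. The plan's own figures.**
- Lower end: 50 / 3 = 16.67, rounded up to 17.
- Upper end: 70 / 1 = 70 per sensor.
- Maximum: 2 sensors × 70 = 140.

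All three reproduce. The range runs from three pairs per infant on both sensors (17) to one pair per infant on one sensor (140).

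**2. What exactly 17 infants yield per sensor, before exclusions.**
- Both sensors at 3 draws: 17 × 3 = 51.
- One infant lost entirely: 16 × 3 = 48.
- One infant giving a single pair per sensor: 16 × 3 + 1 = 49.
- Both sensors, 2 draws each: 17 × 2 = 34.
- One sensor per draw, alternated over 3 draws: 51 / 2 = 25.5, so 25 or 26.
- One pair per infant: at most 17.

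**3. Loss tolerance at 17 infants.** The slack is 51 − 50 = 1 pair, and 1 / 51 = 2.0%. If pairs are lost independently and p is the chance that a pair is valid, P(at least 50 of 51) = p^51 + 51 × p^50 × (1 − p).

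| Assumed loss | Expected valid pairs | P(≥ 50 on one sensor) |
|---|---|---|
| 1% | 50.5 | 0.91 |
| 2% | 50.0 | 0.73 |
| 5% | 48.5 | 0.27 |
| 10% | 45.9 | 0.03 |

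These chances apply only if all 51 pairs are collected and enrolment then stops at exactly 17. Clustered losses would change them.

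**4. Infants needed to reach 50.** With both sensors at all 3 draws, an expected 50 valid pairs needs 50 / (3 × (1 − loss)), rounded up: 18 at 5% loss, 19 at 10%, 21 at 20%, 24 at 30%. For at least a 90% chance of 50 on one sensor, the numbers are 19, 20, 23 and 27. With no loss but fewer pairs per infant per sensor: 50 / 2 = 25 infants at 2 pairs, 50 / 1.5 = 34 (rounded up) at 1.5, and 50 at 1 pair. If that one pair is on one sensor only, both sensors together need 100. All of these lie between 17 and 140.

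**5. Room under the maximum.** At one pair per infant, split equally, 140 / 2 = 70 per sensor. The tolerable loss is (70 − 50) / 70 = 28.6%. Higher yields per infant leave more.

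**6. Effect of a shortfall on precision.** Taking the standard error as proportional to 1/√n:
- 49 instead of 50: √(50/49) = 1.01, about 1% wider.
- 45.9 instead of 50: √(50/45.9) = 1.04, about 4% wider.
- 34 instead of 50: √(50/34) = 1.21, about 21% wider.
- 25.5 instead of 50: √(50/25.5) = 1.40, about 40% wider.

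The last two require enrolment to halt at 17 with the Section 10.2 target plainly missed. If the pairs are made up by adding infants who each give fewer, precision is no worse when errors within an infant are positively correlated.

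**The case for a change.** The strongest case for a change is that Section 10.2 only says the study is targeted to obtain 50 to 70 pairs, while the synopsis and Section 4.2 give 17 to 140 with no pair count. With no hypothesis test, the pair count carries the whole justification of the sample size. One sentence tying enrolment to evaluable pairs per sensor would cost little.

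Part of this stands. The documents do not state the counting rule. They also do not say whether the alternation note in Section 5.3 is meant only for collections with a single sensor; three pairs per sensor from at most three draws requires both sensors at every draw. Reading the adequacy sentence as per sensor is an inference too, though the target sentence beside it and the separate analyses in Section 10.3.3 make it the natural one.

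The harm does not stand. It requires the sponsor to treat a minimum as a stopping point, which no section does, and to disregard the per-sensor target in the same section. Nor must a shortfall stay hidden until enrolment closes. The study is open label (Section 3.3), electronic data go to the sponsor (Section 11.1.1), and monitoring visits follow progress (Section 12). Pairs can be counted as they accrue. Writing 34 in place of 17 would be no improvement, since it presupposes one reading of the alternation note.

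**Conclusion.** No change to the plan follows. The figure of 17 is arithmetically right, and it is what it claims to be: the fewest infants who could supply 50 pairs per sensor, with a tolerance of one pair in 51. The allowance for lower yield and for exclusions lies in the rest of the range, up to 140, which still gives 70 pairs per sensor at one pair per infant and withstands 28.6% loss.

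The missing counting rule is a detail that analysts fill sensibly. Because Section 10.3.2 restricts the analysis to valid data and Section 10.3.3 analyses and reports each sensor with its number of pairs, the natural count is evaluable pairs per sensor, with enrolment continuing until each reaches 50. A sponsor following Section 10.2 as written would get there. The alternation note fits the three-pair maximum if it governs single-sensor collections, and that is a procedural reading rather than a flaw in the sample size.

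The conclusion assumes that the target is per sensor, that enrolment follows the pair target and not the subject minimum, and that losses at one pair per infant stay below 28.6%. A near miss would cost little: about 1% in standard error at 49 pairs and about 4% at 45.9, in a descriptive estimate with no test attached.
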